## 5.12 Post-study therapy

After ending of the clinical trial, patients will receive further standard medical care as usual for this kind of disease.

## 6 **Efficacy and safety variables**

Specific time points for evaluation of efficacy variables and safety measures are given in 4.13.

## 6.1 Measurement target variables

### 6.1.1 Primary target variable

 change of maximal postischemic forearm blood flow during reactive hyperaemia after 5 min of forearm ischemia (FBF max. ml/100ml) at week 20

Additional primary variable for extension period:

pulse wave velocity at EOT after 52 weeks

### 6.1.2 Secondary target variables

- change of area under the FBF curve over 10 cycles of venous congestion (compared to baseline/day 0) at week 20 and EOT Extension
- maximal postischemic skin blood flow (arbitrary units) during reactive hyperaemia after
   5 min of forearm ischemia at week 20 and EOT Extension using LDF
- change of postischemic skin blood flow using LDF (compared to baseline/day 0) at week
   20 and EOT Extension
- pulse wave velocity at 20 weeks and EoT Extension compared to baseline
- laboratory parameter (see above) at week 20 and EOT Extension

### Additional secondary variable for extension period:

 change of maximal postischemic forearm blood flow during reactive hyperaemia after 5 min of forearm ischemia (FBF max. ml/100ml) at EOT after 52 weeks (EOT Extension)

### 6.1.3 Measurement of safety analysis

- major bleeding defined as clinically overt and associated with one of the following:
  - decrease in hemoglobin level of 2 g/l or required transfusion of at least 2 units of red cells or
  - involved a critical organ or
  - was fatal, in accordance with the recommendation of the International Society on Thrombosis and Haemostasis (ISTH).
- clinically relevant non-major bleeding defined at least one of the following signs:
  - spontaneous skin hematoma of at least 25 cm

- spontaneous nose bleeding of more than 5 min duration
- macroscopic hematuria, either spontaneous or, if associated with an intervention, lasting more than 24 h
- spontaneous rectal bleeding (more than spotting on toilet paper)
- gingival bleeding for more than 5 min
- bleeding leading to hospitalization and/or requiring surgical treatment
- bleeding leading to a transfusion of less than 2 units of whole blood or red cells
- any other bleeding event considered clinically relevant by the investigator

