#### Explorative Study Objective(s)

assessment of platelet activation and measurement of mitogenic potential

Study end points	
 
Primary variable         
 
change of maximal postischemic forearm blood flow during reactive hyperaemia after 5 min of forearm ischemia (FBF max. ml/100ml) at 20 weeks
 
 
 
Additional primary variable for extension period:         
 
pulse wave velocity at EOT after 52 weeks
 
 
 

Study end points	
 
Secondary variables
 
change of the area under the postischemic FBF curve over 10 cycles of intermittent venous congestion (compared to baseline) after 20 weeks and EOT Extension
 
maximal postischemic skin blood flow (arbitrary units) during reactive hyperaemia after 5 min of forearm ischemia at 20 weeks and EOT Extension using LDF
 
change of postischemic skin blood flow (compared to baseline) using LDF
 
Pulse wave velocity at 20 weeks compared to baseline)
 
laboratory parameter (see above) at 20 weeks and EOT Extension
 
Additional secondary variable for extension period:
 
change of maximal postischemic forearm blood flow during reactive hyperaemia after 5 min of forearm ischemia (FBF max. ml/100ml) at EOT after 52 weeks (EOT Extension)
 

Safety Parameter	Safety Parameter
	
 
major bleeding defined as clinically overt and associated with one of the following:
 

	
 
reduction of hemoglobin level of 2 g/L or
 

	
 
required transfusion of at least 2 units of red cells or, involved a critical organ or was fatal, in accordance with the recommendation of the International Society on Thrombosis and Haemostasis (ISTH).
 

	
 
clinically relevant non major bleeding defined as at least one of the following:
 

	- spontaneous skin hematoma of at least 25 cm
	
 
spontaneous nose bleeding of more than 5 minutes duration
 

	
 
macroscopic hematuria, either spontaneous or, if associated with an intervention, lasting more than 24 hours
 

	
 
spontaneous rectal bleeding (more than spotting on toilet paper)
 

	
 
gingival bleeding for more than 5 minutes
 

	
 
bleeding leading to hospitalization and/or requiring surgical treatment
 

	
 
bleeding leading to a transfusion of less than 2 units of whole blood or red cells
 

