#### 4.7.3 Adverse Events and Serious Adverse Events

Adverse events and serious adverse events will be collected from first intake of study medication and then at each visit until the end of the study (day 0-week 52).

Bleedings (yes/no). If "yes" bleeding is classified as:

- major bleeding ("major")
- clinically relevant non-major bleeding ("CRNM")

Patients with major bleeding at any time in the course of the study will be counted in the category "major". All patients with CRNM but never "major" at any time will be counted in the category "CRNM". Only patients with minor bleedings but never CRNM are counted in the category "minor".

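### The 2 g/l haemoglobin trigger for major bleeding does not fit the plan's own severity tiers, so some lesser overt bleeds can be counted as major

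*Protocol*

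**What the plan says.** Protocol 6.1.3 opens the definition with "major bleeding defined as clinically overt and associated with one of the following". The criteria are joined by 'or': "decrease in hemoglobin level of 2 g/l or required transfusion of at least 2 units of red cells or" critical-organ involvement or a fatal outcome. The section says that the definition follows the ISTH recommendation, but neither document prints the ISTH figure. The synopsis (Safety Parameter) has "reduction of hemoglobin level of 2 g/L or", so value and unit agree in both places.

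The clinically relevant non-major (CRNM) list in 6.1.3 includes "bleeding leading to hospitalization and/or requiring surgical treatment" and "bleeding leading to a transfusion of less than 2 units of whole blood or red cells". It also has items defined by signs alone, such as "spontaneous nose bleeding of more than 5 min duration". No item carries a haemoglobin condition, and nothing says that CRNM excludes bleeds that meet a major criterion.

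SAP 4.7.3 does not restate the threshold. Its counting rule is by patient: "Patients with major bleeding at any time in the course of the study will be counted in the category" for major bleeding, and CRNM is reserved for patients who were never major.

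**The concern.** The definition looks out of scale with itself. A 2 g/l fall stands as an equal alternative to a transfusion of 2 or more units, while a bleed needing a smaller transfusion, admission or surgery sits one tier lower. If those lower-tier bleeds usually come with a 2 g/l fall, they satisfy both definitions. The size of the trigger also raises the question of whether a trivial overt bleed could become major through measurement and day-to-day variation alone.

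Bleeding carries weight in this trial. Protocol 2.5 calls it the major risk of anticoagulation, 2.3 lists major bleeding among the secondary objectives, 3.6 has the DSMB advise on continuation, and 4.10 names increased bleeding as a possible ground for closure. The SAP bleeding table (7.8.4) compares the arms with a p-value. If a share of lesser bleeds is moved up, the major row partly reflects the number of overt bleeds of any kind, and the CRNM row is too low.

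**Working it through.** **1. Is there a figure to reproduce?** No. The 2 g/l is a definition; no sample size, power or error rate rests on it.

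**2. The tiers side by side (Protocol 6.1.3).**

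| Feature of an overt bleed | Tier as listed | Also major if haemoglobin falls 2 g/l? |
|---|---|---|
| Transfusion, 2 units or more | Major | Already major |
| Transfusion, under 2 units | CRNM | Yes |
| Admission or surgery | CRNM | Yes |
| Signs only (nose, gum, rectal, haematuria, haematoma) | CRNM | Yes, if an associated fall is recorded |

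The right-hand column follows from the 'or' in the major definition. That a transfused or hospitalised bleed would be expected to show such a fall is a judgement; the documents do not state it.

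**3. What comparison defines the fall?** None is given. SAP 4.7.2 schedules haemoglobin on day 0 and at weeks 2, 8, 20, 28, 36 and 52, and the Protocol 4.12.2 schedule adds a screening sample. Protocol 4.15.1 assigns safety parameters to each site's local laboratory. No reference value, time window or assay precision is stated.

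**4. How often would chance produce the fall?** Let s be the SD of a single haemoglobin value in one patient, biological plus analytical. The documents do not give s; 1 to 5 g/l is assumed. The trigger is read as a fall of 2 g/l or more. For two independent normal values the difference has SD √2·s, so

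P(observed fall ≥ 2) = Φ((true fall − 2)/(√2·s)).

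With no true change and s = 3, this is Φ(−2/4.243) = Φ(−0.471) = 0.319. Over the range:

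| Assumed s (g/l) | No true fall | True fall 5 g/l | True fall 10 g/l |
|---|---|---|---|
| 1 | 7.9% | 98.3% | 100.0% |
| 2 | 24.0% | 85.6% | 99.8% |
| 3 | 31.9% | 76.0% | 97.0% |
| 4 | 36.2% | 70.2% | 92.1% |
| 5 | 38.9% | 66.4% | 87.1% |

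The true falls of 5 and 10 g/l are illustrations, not figures from the documents.

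**5. Reading the result.** Of 100 trivial overt bleeds, each with one before/after pair and no real loss, about 8 to 39 would meet the trigger (24 to 39 for s of 2 to 5). The chance is 50% when the true fall is exactly 2 g/l and passes 50% only above that. A bleed with a real fall of 5 to 10 g/l meets the trigger in roughly 66% to 100% of cases, whichever CRNM item it also satisfies. On an assumed haemoglobin of 130 to 150 g/l, the trigger is 2/150 = 1.3% to 2/130 = 1.5% of the level.

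**The case against.** The strongest reply is that the trigger never acts alone. A bleed must be clinically overt and the fall must be associated with it, so a chance drop in a patient who has not bled counts for nothing. This stands, and it limits every percentage above to patients with an overt bleed.

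It also disposes of a stronger reading. A reader might compare every scheduled sample with day 0. By simulation with independent normal errors, at least one of the three post-baseline values to week 20 would then lie 2 g/l or more below baseline by chance in about 18% to 64% of patients (s of 1 to 5), and at least one of six to week 52 in about 27% to 77%. But neither document says that any scheduled sample may be matched to any bleed, or that day 0 is the reference. Those figures show what the missing time window could allow, not what the plan prescribes.

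A second reply is that the SAP settles the overlap, since a patient who meets both definitions is counted once. That is true of double counting, but the rule always resolves toward major, which is the direction at issue.

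A third is that bleeding is outside both primary endpoints and the sample-size calculation. This is also true, but it remains the main safety comparison.

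Finally, the assumed SDs have no source in the documents, and at s = 1 the chance effect is modest. That stands as well. The overlap between the tiers does not depend on s.

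**Conclusion.** Wrong as written (decision threshold). The 2 g/l trigger does not fit the tier structure around it: bleeds listed as non-major can meet the major definition, and the SAP then counts the patient as major. Chance alone would lift about 8% to 39% of trivial overt bleeds on a single before/after pair, assuming a single-value SD of 1 to 5 g/l and independent normal errors.

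Three further inferences are tempting but unsupported:

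- **That most overt bleeds become major and the non-major tier empties.** On one pair, 39% is the top of the chance range. Sign-based bleeds without a recorded associated fall stay CRNM, so the tier shrinks but remains.
- **That the figure is a unit slip of a known factor.** The internal mismatch suggests that the trigger may be too small, but not by how much, and the ISTH figure is not printed.
- **That the results could not be compared with other trials using the cited definition.** This too needs the unprinted figure.

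**What to change.** - Check the value and the unit in Protocol 6.1.3 and the synopsis against the ISTH recommendation they cite, and reconcile both places. No replacement threshold is proposed here.
- State which haemoglobin value is the reference and within what time of the bleed the fall must be seen.
- State that CRNM means a bleed that meets none of the major criteria.
- Write the reconciled definition into SAP 4.7.3, so that the bleeding analysis in 6.12.4 and the table in 7.8.4 rest on it.
- Re-assess the bleeds already classified.

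The text change is small: two places in the protocol, by amendment under section 12.1, and one in the SAP. SAP 4.8 derives no bleeding variable, so the re-assessment may mean reviewing individual events rather than re-running a program. Its cost depends on the number of bleeds recorded. Scheduled haemoglobin values are already collected, so no new visits are needed.

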### 6.1.4 Rationale for assessment procedures

All parameters evaluated in this study as well as the methods to measure them, are standard variables / methods in clinical practice or non-invasive techniques. They are widely used and generally recognized as reliable, accurate and relevant.

## 6.2 Applied measurement procedures

### 6.2.1 Venous occlusion plethysmography for assessment of forearm blood flow FBF:

Endothelium dependent vasodilation of resistance vessels will be assessed in both arms simultaneously using strain-gauge venous occlusion plethysmography (Gutmann Medizinelektronik, Eurasburg, Germany or Hokanson Pletysmograph EC6). Patient rest for at least 20 min in supine position in a temperature controlled room. At both upper arms a cuff for venous occlusion will be placed. On the forearm, at the side of its maximal circumference an elastic straingauge is used to assess changes of the forearm circumference after release of the upper arm cuff. At start of each assessment of postischemic vasodilation the upper arm cuff will be inflated to 20 Torr above the arterial blood pressure (but at least 200 Torr) for 5 min to induce forearm ischemia. Thereafter the upper arm cuff will be released for free arterial blood inflow into the forearm. Every 10 sec the upper arm cuff inflates automatically to 40 Torr to induce venous congestion for about 10 sec. These sequences will be repeated 10 times. During venous congestion the arterial blood inflow into the forearm causes an increase of its circumference which depends on the amount of blood inflow. The latter one is determined by forearm vascular resistance due to the arteriolar tense.

### 6.2.2 Laser Doppler Fluxometry:

The technique of micro-lightguide spectrophotometry and laserdopplerfluxometry (LDF) will be used to measure microvascular skin blood flow and postcapillary tissue oxygenation (sO2) at the lower forearm. LDF skin probes will be placed at the lower forearm and on the thenar surface of the left hand in between the phalanx of the thumb and the metatarsale of Dig II, directly adjacent to the muscle abductor pollicis. Microvascular blood flow and post-capillary sO2 will be measured

in parallel in a tissue depth of 2 mm and 8 mm. Via a cuff on the upper arm a supra-systolic occlusion will be induced for 4 minutes, and thereafter, the postischaemic microvascular blood flow and sO2 will be recorded as a measure of microvascular endothelial function in the skin. Pulse wave velocity and arterial stiffness:

Measurements will be performed using the Mobil-O-Graph device (IEM Inc., Stolberg, Germany). This device allows the non-invasive oscillometric analysis of blood pressure and pulse wave over 24 hours. Based on pulse wave analysis we calculate the aortic augmentation index as marker of arterial stiffness and pulse wave velocity. The Mobil-O-Graph device has been validated against gold standard procedures such as applanation tonometry (SphygmoCor, AtCor Inc.) and is used in clinical routine.

6.2.3 Pulse wave velocity and arterial stiffness:

Measurements will be performed using the Mobil-O-Graph device (IEM Inc., Stolberg, Germany). This device allows the non-invasive oscillometric analysis of blood pressure and pulse wave over 24 hours. Based on pulse wave analysis we calculate the aortic augmentation index as marker of arterial stiffness and pulse wave velocity. The Mobil-O-Graph device has been validated against gold standard procedures such as applanation tonometry (SphygmoCor, AtCor Inc.).

Each investigator will receive a user manual for the correct application of the techniques.

## 7 Administrative aspects

### 7.1 Data documentation

### 7.1.1 eCRF

All data relevant to this trial are to be documented by the responsible investigator in a web-based eCRF immediately after measurement has been taken. Entering data may be delegated to members of the trial team but the investigator will have to check and sign the eCRF entries. Serious Adverse Event Forms have also to be signed and dated by the investigator.

## 7.2 Data management

The IT infrastructure and data management staff will be supplied by GWT. The trial database will be developed and validated prior to data entry based on standard operating procedures at GWT. The data management system is based on commercial trial software (Macro 4.0) and stores the data in a database, storing all changes in an audit trail. The trial software has a user and role concept that can be adjusted on a trial-specific basis. The database is integrated into a general IT infrastructure and safety concept with a firewall and backup system. A regularly backup of all trial data will be performed by InferMed (London). After completion and cleaning of data, the database is locked and the data exported for statistical analysis.

Trial sites will enter data online via Internet. Plausibility checks are run during data entry, thereby detecting discrepancies immediately. The GWT Data Management will conduct further checks for completeness and plausibility and will clarify any questions with the trial sites electronically via trial software. Discrepancies and implausible values will be clarified in writing between the data manager and the trial site. These electronic queries have to be answered by the trial site without unreasonable delay.

Further details will be specified in the data management manual.

## 7.3 Data quality

## 7.3.1 Monitoring

The trial site will be monitored to ensure the quality of the data collected. The objectives of the monitoring procedures are to ensure that the trial subject's safety and rights as a study participant are respected, that accurate, valid and complete data are collected, and that the trial is conducted in accordance with the trial protocol, the principles of GCP and local legislation.

All investigators agree that the monitor will regularly visit each trial site and assure that the monitor will receive appropriate support in his activities at the trial site, as agreed in separate contracts with each site. The declaration of informed consent includes a statement to the effect that the monitor has the right – while observing the provisions of data protection legislation – to compare the eCRFs with the trial subject's medical records (physicians notes, laboratory printouts etc.). The investigator will ensure access for the monitor to all necessary documentation for trial-related monitoring. The purposes of the monitor visits are as follows:

- check the informed consent
- check inclusion and exclusion criteria
- monitor trial subject safety (occurrence and documentation/reporting of AEs and SAEs)
- check the completeness and accuracy of entries on the eCRFs
- validate the entries on the eCRFs against those in the source documents (source data verification)
- perform drug accountability checks
- evaluate the progress of the trial
- evaluate compliance with the trial protocol
- assess whether the trial is being performed according to GCP at the trial site
- discuss with the investigator aspects of trial conduct and any deficiencies found.

Monitoring at each trial site will be done for 100 % for the ISF, the patient's informed consent, all in- and exclusion criteria, safety parameters and the drug accountability.

Source data, pre-exisiting disease as well as concomitant medications and disease will be monitored for 50 % of the patient data. Monitoring will be adapted to the quality of data recorded by the trial site. Monitoring activities will also be adapted to pre-visit checks of the data entered to the eCRF or by telephone visits.

A monitoring visit report will be prepared for each visit describing the progress of the clinical trial and any problems (e.g. refusal to give access to documentation). A follow-up letter will be prepared for the trial site after each visit.

Further details will be given in the Monitoring Manual.

## 7.3.2 Data quality assurance

The responsibilities of the German Investigators are set out in the German drug law (AMG), GCP-Verordnung (GCP-V), the ICH guideline for Good Clinical Practice (ICH-GCP) and in the Directive 2001/20/EC of the European Union.

## 7.3.3 Audits/Inspections

As part of quality assurance, the sponsor has the right to audit the trial site and any other institutions involved in the trial. The aim of an audit is to verify the validity, accuracy and completeness of data, to establish the credibility of the clinical trial, and to check whether the trial subject's rights and trial subject safety are being maintained. The sponsor may assign these activities to persons otherwise not involved in the trial (auditors). These persons are allowed access to all trial documentation (especially the trial protocol, case report forms, trial subjects' medical records, drug accountability documentation, and trial-related correspondence).

In addition, inspections by regulatory health authority representatives and IEC are possible. The investigator should notify the sponsor immediately of any such inspection.

The investigator/institution agrees to allow the auditor or inspector direct access to all relevant documents and allocate his/her time and the time of his/her staff to the auditor/inspector to discuss findings and any issues. Audits and inspections may occur at any time during or after completion of the study.

All persons conducting audits will keep all trial subject data and other trial data confidential.

### 7.3.4 Archiving

All study relevant data, informed consent forms and other important trial materials will be archived for at least 10 years in accordance with §13 Sec. 10 of the national GCP Regulations.

Essential documents shall be archived safely and securely in such a way that ensures that they are readily available upon authorities' request.

Patient (hospital) files will be archived according to local regulations and in accordance with the maximum period of time permitted by the hospital, institution or private practice. Where the archiving procedures do not meet the minimum timelines required by the sponsor, alternative arrangements must be made to ensure the availability of the source documents for the required period.

The investigator/institution notifies the sponsor if the archival arrangements change (e.g. relocation or transfer of ownership).

The ISF is not to be destroyed without the sponsor's approval. The investigator's contract will contain all regulations relevant for the study center.

## 8 Ethical and regulatory aspects

## 8.1 Independent ethics committee

The protocol, ICF and any other supporting study documents will be reviewed by the independent ethics committee (IEC) of the State Chamber of Physicians of Saxony (*Sächsische Landesärztekammer*) prior to study initiation as the leading IRB. Each study site may not begin the study until the responsible authority/committee for that site has given its written approval, signed by the authority chairperson or authorized personnel, and a copy of the approval letter and the approved ICF for that site has been provided to the Investigator.

